**Investigational agent**

External Beam Radiation Therapy (EBRT)

**IND Number**

*N/A*

**Historical Protocol Versions**

Version 1: 21JUL2017

Version 2: 12APR2018

Version 3: 08JUN2018

Version 4: 03MAY2019

Version 5: 16AUG2019

Version 6: 15SEP2020

Version 7: 23NOV2021

## LIST OF ABBREVIATIONS

Abbreviation or Term 	Definition/Explanation
AE	Adverse event
ALT	Alanine aminotransferase
ANCOVA	Analysis of covariance
ANOVA	Analysis of variance
APTT	Activated partial thromboplastin time
AST	Aspartate aminotransferase
AV	Atrioventricular
β-HCG	Beta-human chorionic gonadotropin
BID	Twice daily
BLQ	Below limit of quantification
BMI	Body mass index
BP	Blood pressure
BUN	Blood urea nitrogen
Ca ++	Calcium
CBC	Complete blood count
CFR	Code of Federal Regulations
CHF	Congestive heart failure
CI	Confidence interval
Cl-	Chloride
CL cr	Creatinine clearance
C max	Maximum observed concentration
C min	Trough observed concentration
CNS	Central nervous system
CR	Complete response
CRF	Case report form
CT	Computed tomography

Protocol name: NOVEMBER (Novem- (9), BrEast Radiation), A Phase II trial of a 9 day course of whole breast radiotherapy for early stage breast cancer.

Version Date: 23NOV2021

Principal Investigator: [name]

Abbreviation or Term^1	Definition/Explanation
CTCAE	Common Toxicity Criteria for Adverse Events
CV	Coefficient of variation
CYP	Cytochrome P450
D/C	Discontinue
ECOG	Eastern Cooperative Oncology Group
eCRF	Electronic case report form
DLT	Dose Limiting Toxicity
ECG	Electrocardiogram
Eg	Exempli gratia (for example)
FACS	Fluorescence Activated Cell Sorting
FDA	Food and Drug Administration
FDG-PET	Fluorodeoxyglucose (FDG)-positron emission tomography (PET)
GCP	Good Clinical Practice
GFR	Glomerular filtration rate
GGT	Gamma glutamyl transferase
GLP	Good laboratory practice
HBsAg	Hepatitis B surface antigen
HBV	Hepatitis B virus
HCO 3 	Bicarbonate
HCV	Hepatitis C virus
HIV	Human immunodeficiency virus
HR	Heart rate
Hr	Hour or hours
IC 50	Half maximal inhibitory concentration
i.e.	Id est (that is)
IEC	Independent ethics committee
INR	International normalized ratio

Protocol name: NOVEMBER (Novem- (9), BrEast Radiation), A Phase II trial of a 9 day course of whole breast radiotherapy for early stage breast cancer.

Version Date: 23NOV2021

Principal Investigator: [name]

Abbreviation or Term^1	Definition/Explanation
IRB	Institutional review board
IU	International unit
IV	Intravenous, intravenously
LDH	Lactate dehydrogenase
LLQ	Lower limit of quantitation
MedRA	Medical Dictionary for Drug Regulatory Activities
MRI	Magnetic resonance imaging
MRSD	Maximum recommended starting dose
MTD	Maximum tolerated dose
NOAEL	No-observed-adverse-effect level
NOEL	No-observed-effect-level
PD	Pharmacodynamic(s)
PFS	Progression Free Survival
PK	Pharmacokinetic(s)
PO	Per os (administered by mouth)
PR	Partial response
PT	Prothrombin time
PTT	Partial thromboplastin time
QC	Quality control
RBC	Red blood cell
QD	Once daily
QTc	QT interval corrected
QTcF	QT interval corrected using Fredericia equation
SAE	Serious adverse event
SD	Standard deviation or stable disease
T 1/2	Terminal elimination half-life
T 3	Triiodothyronine

Protocol name: NOVEMBER (Novem- (9), BrEast Radiation), A Phase II trial of a 9 day course of whole breast radiotherapy for early stage breast cancer.

Version Date: 23NOV2021

Principal Investigator: [name]

Abbreviation or Term^1	Definition/Explanation
T 4	Thyroxine
T max	Time of maximum observed concentration
TID	Three times daily
TSH	Thyroid-stimulating hormone
ULN	Upper limit of normal
ULQ	Upper limit of quantitation
UV	Ultraviolet
WBC	White blood cell
WOCBP	Women of childbearing potential
WONCBP	Women of non-childbearing potential

All of these abbreviations may or may not be used in protocol.

Protocol name: NOVEMBER (Novem- (9), BrEast Radiation), A Phase II trial of a 9 day course of whole breast radiotherapy for early stage breast cancer.

Version Date: 23NOV2021

Principal Investigator: [name]

## STUDY SUMMARY

Title	NOVEMBER (Novem- (9), BrEast Radiation), A Phase II trial of a 9 day course of whole breast radiotherapy for early stage breast cancer.
Short Title	NOVEMBER.
Protocol Number	IRB#103976
IND	N/A
Phase	Phase II
Design	Single arm non-inferiority trial
Study Duration	8 years (3 years enrollment, 5 years follow-up)
Study Center(s)	Single-center at Huntsman Cancer Institute
Objectives	
Primary objective will be to evaluate 24 month breast photographic cosmetic scores with 9 fraction hypofractionated radiation compared to published hypofractionation radiation.
 
Secondary objectives include evaluation of patient reported outcomes, radiation toxicities, disease recurrence, and cost effectiveness.

Number of Subjects	102 enrolled for at least 87 evaluable
Diagnosis and Main Eligibility Criteria	Stage 0-IIIB breast cancer in the setting of breast conservation. Exclusion: Prior RT, Recurrent setting, Node positive, NO chemo before RT, No pregnancy
Study Product, Dose, Route, Regimen	External Beam Radiation Therapy (EBRT)
Duration of administration	9 days of Radiation (11-14 calendar days)
Reference therapy	Study therapy will be compared with published phase III data on 15 day, & 16 day hypofractionation breast RT studies from the UK and Canada.
Statistical Methodology	The primary analysis will be a one sample t-test. The null hypothesis will be that the true rate is good to excellent photographic breast cosmetic assessment in $\leq 70\%$ of patients. The one sided alternative hypothesis is a good to excellent photographic breast cosmetic assessment in $> 70\%$ of patients. Assuming the true rate is 80% (e.g. exact equivalence), a sample of 87 evaluable subjects will provide 80% power at the alpha = 0.1 significance level.

[figure not shown]
Protocol name: NOVEMBER (Novem- (9), BrEast Radiation), A Phase II trial of a 9 day course of whole breast radiotherapy for

early stage breast cancer.

Version Date: 23NOV2021

Principal Investigator: [name]

## STUDY SCHEMA

\*Regional Nodes will not be specifically targeted, however some level I/II nodes may be incidentally covered. Nodal evaluation requirement waived for selected patients (Section 5.1).

Patients will be followed with clinical visits for 3 years or until death, whichever comes first. Data at 5 years will be by chart review only.

Please refer to the full protocol text for a complete description of the eligibility criteria and treatment plan.

Protocol name: NOVEMBER (Novem- (9), BrEast Radiation), A Phase II trial of a 9 day course of whole breast radiotherapy for early stage breast cancer.

Version Date: 23NOV2021

Principal Investigator: [name]

## 1 OBJECTIVES

### 1.1 Primary Objectives and Endpoint

1.1.1 To evaluate 24 month breast photographic cosmetic scores with 9 fraction radiation compared to standard hypofractionation.

### 1.2 Secondary Objectives and Endpoint

1.2.1 To evaluate Breast-Q Patient Reported Outcomes (PROs) compared to historical control in breast conservation.

1.2.2 To evaluate the incidence of acute and late radiation complications, based on CTCAE 4.0 toxicity.

1.2.3 To evaluate the local and local regional recurrence rate.

1.2.4 To compare the direct and indirect patient costs for radiation therapy compared to historical controls as well as quality adjusted life years, utilizing the Breast-Q Patient Reported Outcomes (PROs) and the EQ-5D.

## 2 BACKGROUND

### 2.1 Rationale for the Study

Adjuvant radiation therapy (RT) plays an important role in successful breast conservation in early stage breast cancer, and has been shown to significantly reduce the risk of breast cancer recurrence over surgery alone. Adding breast radiation to lumpectomy has allowed women to keep their natural breast, as multiple randomized trials have demonstrated equivalent overall and disease free survival compared to a mastectomy. Meta-analyses have concluded that post lumpectomy radiation improves breast cancer survival, with an estimated 1 life saved for every 4 recurrences prevented. An important component of radiation therapy is the time-dose-fractionation schedule. Up until the last decade, the standard radiation schedule in North America involved 6-8 weeks of daily radiation.

In 1986 Royal Marsden Hospital and the Gloucestershire Oncology Centre collaborated in a prospective trial evaluating 3 breast fractionations: 50Gy in 25 fractions, 39Gy in 13 fractions (3.0Gy/fx), or 42.9Gy in 13 fractions (3.3Gy/fx) all over 5 weeks . In 1999, after over 1400 patients had been enrolled the trial design was expanded into a multi-institutional trial and patient data from the earlier study was rolled into what became START A, with the 13 fraction regimen changed to 3.2Gy/day for 41.6Gy. A total of 2236 women were randomized to one of three arms between 1986 and 1999, treating patients with 2D planning and Cobalt-60. The overall treatment time of 5 weeks was kept constant in all three arms. The primary endpoint was late breast change. Local control

was a secondary endpoint. Locoregional relapse was non-significantly different in the 3 arms at 10 years at 7.4%, 6.3% and 8.8%. Fourteen percent of patients received CMF chemotherapy. Running in parallel to STARTA, the UK STARTB trial was an accelerated hypofractionation trial comparing 50Gy in 2Gy daily fractions for 5 weeks versus 40Gy delivered in 2.67Gy daily for 15 days. This trial accrued 2215 stage I and II breast cancer patient between 1999 and 2001, treating patients with Cobalt-60, utilizing 2D planning. 23% of patients received chemotherapy +/- tamoxifen. In 1993, shortly after the RMH began their prospective trial, researchers with the National Cancer Institute of Canada (NCIC) and Ontario Clinical Oncology Group conducted a similar hypofractionated randomized trial comparing whole breast radiation of 50 Gy in 25 fractions versus a hypofractionated regimen 42.5 Gy in 16 fractions. 10 year data was published by Whelan et al in 2010 revealing equivalent outcomes in terms of cancer control and toxicity. Cosmesis was identical with excellent or good scores at 3 and 5 years in 77% of patients in both groups. Toxicities were comparable. Grade 2 and 3 toxicities were negligible. At 5 years, 87% of women in the experimental arm had no skin toxicity, and 66% of women had no subcutaneous toxicity, compared with 82% and 60% in the control arm, respectively. A major limitation of the Canadian study is the lack of a lumpectomy boost. The addition of an extra dose of radiation to the lumpectomy cavity, called a boost, has been shown in 2 randomized trials to significantly reduce further the risk of a local breast recurrence. Women in the NCIC study were not allowed a breast lumpectomy boost, but the UK start trials allowed an optional boost of 14Gy in 5 daily fractions. This occurred in 61% of patients in STARTA and 43% in STARTB. Adding a lumpectomy cavity boost in a sequential manner, adds an additional 5-8 treatment days of radiation, significantly increasing treatment burden. Several institutions have published results suggesting the safety of delivering the lumpectomy cavity boost concurrent with the whole breast radiation. From 2011-2015, the Radiation Therapy Oncology Group (RTOG) moved this single institution data into the phase III randomized trial 1005, randomizing women with a sequential vs. concurrent lumpectomy cavity boost. In this trial, the whole breast radiation could be administered in 15 vs. 25 fractions, at the discretion of the treating physician. In the concurrent arm, the breast received the UK START dose of 40Gy (2.66/day) while the lumpectomy cavity received an additional daily dose, resulting in a total of 48Gy delivered, 3.2Gy/day. In the conventional arm, the breast received the boost delivered over an additional 6-7 daily treatments as the treating physician discretion. The UK has tried to advance the hypofractionation concept further with the UK Fast trial. This trial enrolled 915 patients from 2004 to 2007 into one of three treatment arms: 50Gy in 25 fractions, 28.5Gy in 5 fractions or 30Gy in 5 fractions, all delivered over 5 weeks. The primary endpoint for the trial is change in photographic breast appearance. Initial publication in 2011, with a mean follow up of 3 years, has shown all arms acceptable in regards to conventional toxicity. The 50Gy and 28.5Gy arms appear to be similar in 2 year photographic appearance, however the 30Gy arms appears to be inferior with a risk ratio of mild to marked change in appearance 1.7:1 (1.26-2.29, p<0.001). There are two potential problems with this hypofractionation model. The radiobiology is not well understood when taking 6 days off between each treatment fractions, therefore the long term disease control outcomes will need to be carefully followed over the next 5-10 years

to ensure equivalent cancer control. Additionally, for women residing a long distance from the nearest treatment facility, this results in additional burden for housing and transportation.

With the publishing of the hypofractionated data from the UK and Canada, there has been an increasing adoption rate of short course radiation here in the US, despite some reluctance. This is likely due to the difficulty some physicians have with changing 30+ years of tradition, as well as the decreased reimbursement rates that come with hypofractionation, given the current fee for service payment model.

We feel our proposed fractionation will provide a significant improvement in convenience and cost effectiveness, while delivering equivalent cancer control.

## 2.2 Baseline Toxicity from whole breast radiation

In reviewing toxicity data from previous hypofractionation trials, the UK STARTB 40Gy in 15 fraction treatment arm (majority received an optional 10Gy boost) reported a 5 and 10 year local recurrence rate of 2% and 3.8% (respectively), and 10 year 4.3% local-regional relapse (3.2-5.2%, CI). Reported toxicities are shown in the table below. Cosmetic results overall were better in the 3 week 40Gy hypofractionation arm compared to the 5 week 50Gy standard arm.

Symptomatic rib fracture	2.2%
Lung fibrosis	1.7%
Ischemic heart disease	1.5%
Breast edema	5%
Telangiectasia	4.2%
Breast shrinkage	26%
Breast induration	14%

In the NCIC hypofractionation randomized study the local recurrence rate (invasive only) at 5 and 10 years was 2.8% and 6.2%. Grade 3 RT associated morbidity was 4%. 30% of women had less than an excellent or good cosmetic result (grade 2 or 3 on the EORTC photographic assessment). This slight higher recurrence rate compared to the UK start data may reflect a higher risk group or the fact the NCIC patients did not receive a lumpectomy cavity boost.

Based on this information, we feel that a reasonable expected combined radiation grade 2 or greater non-acute toxicity rate (non-cosmetic) would be 7-10%, a conservative estimate from several prospective trials.

Also based on this information, we feel that a reasonable expected local recurrence rate would be 5-6%, with an upper limit of 10% acceptable.

### 2.3 Altered Fractionation in Breast Cancer

In standard breast irradiation, daily fraction sizes of 180 cGy or 200 cGy are commonly used and are described as conventional or standard. The rationale for conventional fractionation and the relationship between fraction size and tissue response is well described by the  $\alpha/\beta$  ratio in the linear quadratic model of fractionation sensitivity. In this empiric model, “late-reacting” normal tissues such as fibroblasts and neurons have a low  $\alpha/\beta$  ratio (2-5 Gy) and are very responsive to increases in fraction size, while “acutely-reacting” normal tissues such as intestinal epithelium have a high  $\alpha/\beta$  ratio (>7 Gy) and are less responsive to changes in fraction size. The biological effect of a given fractionation scheme size is related to the  $\alpha/\beta$  ratio by the equation:

$$\text{Biological Effective Dose} = \text{BED} = nd \left(1 + \frac{n}{\alpha/\beta}\right) \text{ where}$$

d = dose/fraction

n = # of fractions

Although relatively high cumulative doses of radiation are needed for tumor control, the daily fraction size has to be respectful of the fraction sensitivity of normal tissues in the treated volume. Accounting for these assumptions, increases in fraction size have to be compensated for by reductions in cumulative radiation dose, which typically are insufficient for tumor control. As a result, daily fractions of 1.8 to 2 Gy are delivered over 4-6 weeks to reach a cumulative dose of 45-60 Gy. In vitro experiments in human breast carcinoma cell lines have suggested an  $\alpha/\beta$  ratio of about 4 Gy.

This 9 day radiation treatment design is supported in its safety and efficacy through similar randomized trials in early stage breast conservation, confirming the BED modeling.

Table of Biological Effective doses from different radiation fractionations

		Biological Effective Dose	
	Total dose/fx size	$\alpha/\beta=2$ (normal tissue)	$\alpha/\beta =4$ (breast cancer)
Whole Breast			
NSABP-B06	50Gy/2	100	75
NCIC	42.56Gy/2.66	100	71.2
UK Start B	40Gy/2.66	93	66.4
UK FAST	30Gy/6 (5 wks)	120	75
UK FAST	30Gy/5.8 (5 wks)	110	69
November	34.2Gy/3.8	99.2	66.7
With Lump Boost			
Lyon Boost	60Gy/2	120	90
EORTC Boost	66Gy/2	132	99
UK Start w/Boost	40Gy/2.66 + 10Gy/2	113	81.4
RTG 1005 SIB	48Gy/3.2	125	86
November	39.6Gy/4.4	126.7	83.2

Hopefully, this short treatment schedule will reduce cost while likely improving patient satisfaction for women. The promise of short-course radiation lies in the added

convenience it may offer to patients who otherwise may not be able to receive radiation, and it may also allow earlier sequencing of radiation with systemic chemotherapy.

Although sequencing seems to be unimportant in the context of breast preservation, it may be important in women at higher risk for locoregional recurrence. In this trial, we will require adjuvant chemotherapy to be delivered after radiation. Given the excellent cure rates and low morbidity with current adjuvant radiation therapy technique and fractionation, it is only natural that subsequent improvements in the field take convenience and economic impact into account.

## 2.4 Photographic Cosmetic Assessment

The EORTC Breast Cosmetic Rating system is a blinded digital photographic method that has been utilized in prior radiation studies and shown to be reliable and valid in detecting effects of radiation morbidity. This method compares the radiated breast with the contralateral untreated side and evaluates: Size, shape, location of the areola/nipple, appearance of the surgical scar, skin pigmentation changes, presence of telangiectasia and a global cosmetic score based on all of the factors. Characteristics are graded on a four-point scale: 0, excellent or no difference; 1, good or small difference; 2, fair or moderate difference; and 3, poor or large difference. In the UK Start B analysis of more than 900 patients, the rate of good/excellent photographic cosmetic assessment was 80% at 2 years. In the NCIC analysis of over 1200 patients the 3 year rate of good/excellent cosmetic assessment was 77% (no 2 yr rate given). Based on the NCIC and UK start photographic assessment, we anticipate that our patients will have an overall good-excellent cosmetic score in  $\geq 70\%$  of patients, when compared to their baseline.

## 2.5 Patient Satisfaction and Well-being as Patient Reported Outcomes (PROs)

The assessment of patient-reported outcomes (PROs) in clinical research provides important insight into how therapies impact the daily lives of patients. There is a growing recognition that patient-reported endpoints are critical in oncology trials, particularly when cosmesis and toxicity are likely to be different in the treatment arms. Patient-reported adverse event collection has been shown to be more thorough than collection by provider-report, with consistent underreporting of side effects by providers. Patient-reporting of health-related quality of life has become the gold standard in part because providers have been found to underestimate the pain and distress their patients are experiencing.

In a trial of different radiation schedules, in which cosmesis may be substantially different in the two arms of the study, patient-reported satisfaction and well-being are particularly important. Although short-term differences between the treatment arms may be momentarily relevant to patients, the long-term cosmetic outcomes are most critical, so we have chosen to collect this data at 24 months (and compare to historical controls). In order to avoid burdening patients, we will only administer the Breast-Q survey to patients at baseline, 6, and 24 months. The EQ-5D-3L will be administered at baseline and 2-8 weeks post radiation therapy.

We will be using the Breast Q survey tool to assess patient satisfaction and well-being. This tool has been validated for use in patients after breast conserving therapy to assess well-being and patient satisfaction with results, and is provided free of charge for academic research. Domains for the survey include: satisfaction with breast, adverse effects of

Protocol name: NOVEMBER (Novem- (9), BrEast Radiation), A Phase II trial of a 9 day course of whole breast radiotherapy for early stage breast cancer.

Version Date: 23NOV2021

Principal Investigator: [name]

radiation, psychosocial well-being, physical well-being and satisfaction with information. Cronbach's alphas for the scale range from 0.81 to 0.98, and the BREAST-Q has test-retest reliability, demonstrated by an intra-class correlation coefficient ranging from 0.85 to 0.987. The electronic 2.0 version we will be using was given retrospectively to 3497 women who had undergone a lumpectomy (1622 with adjuvant radiation) and determined to be a reliable and validated survey tool, with median score for Satisfaction with Breast to be 62 (44-77), and no significant difference in the radiated cohort.

We will be using the EQ-5D-3L survey tool. The 3-level version of EQ-5D (EQ-5D-3L) was introduced in 1990 by the [EuroQol Group](#). The EQ-5D-3L essentially consists of 2 pages: the EQ-5D descriptive system and the EQ visual analogue scale (EQ VAS).

The EQ-5D-3L descriptive system comprises the following five dimensions: mobility, self-care, usual activities, pain/discomfort and anxiety/depression. Each dimension has 3 levels: no problems, some problems, and extreme problems. The patient is asked to indicate her health state by ticking the box next to the most appropriate statement in each of the five dimensions. This decision results into a 1-digit number that expresses the level selected for that dimension. The digits for the five dimensions can be combined into a 5-digit number that describes the patient's health state.

The EQ VAS records the patient's self-rated health on a vertical visual analogue scale where the endpoints are labelled 'Best imaginable health state' and 'Worst imaginable health state'. The VAS can be used as a quantitative measure of health outcome that reflects the patient's own judgement.

## 2.6 Cost Effectiveness

We hypothesize that a 9 fraction course will be more cost effective. Costs will be compared to 45 de-identified patients that were treated with a standard hypofractionated regimen of 19 treatments. Direct costs of medical care to each patient will be estimated using utilization information from HCI financial/claims data. Generalized linear models will then be used to model these costs as a function of treatment, time on study, and all available baseline patient characteristics to assess the extent to which estimated direct cost is impacted by the type of radiation dosing. Given the well-known fact that healthcare costs are typically highly skewed, regression models will employ the appropriate distribution and transformation link.

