## 8.4 Economic Analysis

A reduction in number of radiation treatments and thereby number of visits to the radiation therapy department will benefit patients directly, both in terms of reduced direct and indirect healthcare costs. Direct healthcare costs are expected to go down because of an expected reduction in health care utilizations services (e.g., office visits, emergency room visits, inpatient admissions). With short-course treatment patients may be able to take less time off from work and/or return to work faster. Potential improvements in cosmetic-outcomes and side effects of radiation therapy with short-course therapy could also translate into a reduction in utilization of health care services, further enhancing the economic impact of hypofractionation. Indirect costs are also expected to be lower for the intervention arm because patients in this arm are expected to resume normal activities sooner. This in turn would help save family caregiver time as well as the cost of dependent care, which will further add to the saving in indirect costs. Therefore, robust measurement of the patient resources used to receive radiation therapy and utilization of health services is a critical component of this trial.

Patients will be given a diary with question domains to be filled out weekly during radiation therapy in order to help improve recall (Appendix II, III and IV).

We will utilize available CPT code charges generated from the time of registration to 2-8 weeks after the completion of radiation therapy. We will utilize the HCI financial data to estimate reimbursable charges.

Questions are adapted from the Medical Expenditure Panel Survey-Household Component (MEPS-HC) created by

AHRQ ([https://meps.ahrq.gov/survey\\_comp/hc\\_survey/2014/DD111214.pdf](https://meps.ahrq.gov/survey_comp/hc_survey/2014/DD111214.pdf)).

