### 9.2.4 Economic Analysis:

Cost-effectiveness (CE) analysis of hypofractionated radiation versus standard fractionation will be explored using cost data and quality adjusted life years (QALYs) (i.e. effectiveness side). A societal perspective will be applied for the analysis because the direct costs (i.e. resource used) relevant to treatments/intervention, indirect costs (i.e. resource lost such as travel time, lost productivity) and side-effects related costs will be considered. Cost for the intervention will be measured for the cost of therapy, medications, hospitalization and medical visits. Costs for treatments due to side effects will be collected. Patient times spent for treatment, travel and lost productivity will be converted to costs using year 2022 mean adult US wage rate. Because costs related to the intervention will be occurred in different years (for example, 2018~2022), they will be adjusted to year 2022 US dollars using the medical component of the Consumer Price Index. If charged amounts relevant to the treatments are available only (i.e. plan paid amounts or reimbursed amounts are not available), they will be converted to costs by using cost-to-charge ratios. We will not compare charges or costs between institutions. The quality of life (QoL) measures will be based on the BREAST-Q and EQ-5D survey and will be used to calculate Quality Adjusted Life Years (QALYs) for the effectiveness side. Because costs and effects will be measured over multiple years, both costs and effects will be discounted at the rate of 3.5%. We will utilize the EQ-5D and Breast-Q to assist in the QALY analysis. See appendix IV. Once parameters are computed: 1) mean differences in cost and effect between treatments, 2) variances for differences in costs and effects, and 3) covariance between effectiveness and cost difference, the incremental cost-effectiveness ratio (ICER) or incremental net benefits summarizing the monetary value of the intervention will be calculated.

$$ICER = \frac{Cost_{\text{Hypofractionated Radiation}} - Cost_{\text{Standard Fractionation}}}{Effect_{\text{Hypofractionated Radiation}} - Effect_{\text{Standard Fractionation}}}$$

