**NOTE: This section is designed to capture the out of pocket expenses associated with radiation therapy.**

How many hours were spent in total for each radiation treatment (time from leaving home/other accommodation or work to return to home/other accommodation or work)?

\_\_\_\_ (hours)

What is the distance from the radiation treatment facility from home/other accommodation or work? \_\_\_\_ (miles)

Did you commute daily to radiation treatment from your home?  Yes     No

Protocol name: NOVEMBER (Novem- (9), BrEast Radiation), A Phase II trial of a 9 day course of whole breast radiotherapy for early stage breast cancer.

Version Date: 23NOV2021

Principal Investigator: [name]

(If yes), method of transport used to get to the radiation therapy facility (Check all that apply)

Car  Yes  No

(If yes) approximate cost for parking per visit \$\_\_\_\_\_.\_\_\_\_

Did you drive yourself?  Yes  No

Were you driven?  Yes  No

Was it a combination of driving yourself or being driven  Yes  No

Shuttle  Yes  No

(If yes) Approximate cost per visit \$\_\_\_\_\_.\_\_\_\_

Public transport  Yes  No

(If yes) Approximate cost per visit \$\_\_\_\_\_.\_\_\_\_

On foot  Yes  No

Taxi/car service  Yes  No

(If yes) Approximate cost per visit (both ways) \$\_\_\_\_\_.\_\_\_\_

(If no), which of the follow apply (check one):

I was in a health care facility during radiation

I was living with a friend/family member during radiation (answer the commuting questions above)

I stayed hotel, apartment, or similar facility during radiation (answer the commuting questions above)

If hotel, apartment or similar facility, estimated cost of lodging during your radiation treatment \$\_\_\_\_\_.\_\_\_\_

Number of radiation treatments during which at least one other person accompanied patient \_\_\_\_

Number of visits to radiation treatment facility since completing radiation therapy (follow up visits) \_\_\_\_

Protocol name: NOVEMBER (Novem- (9), BrEast Radiation), A Phase II trial of a 9 day course of whole breast radiotherapy for

early stage breast cancer.

Version Date: 23NOV2021

Principal Investigator: [name]

From the 1st day of starting radiation, until 40 days after the completion of radiation:

Number of days the patient was unable to go to work at all \_\_\_\_

Number of days the patient went to work part-time \_\_\_\_

If part time, number of hours reduced from typical work day \_\_\_\_

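### The economic analysis is labelled societal, but its named direct-cost sources are HCI billing only and the survey asks nothing about care or medicines obtained elsewhere

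*Combined protocol and SAP*

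**What the plan says.** Section 1.2.4 makes patient costs and quality-adjusted life years a secondary objective. Section 2.6 hypothesises that 9 fractions will be more cost effective than a 19-treatment course given to 45 comparators, and names the source of direct cost: "Direct costs of medical care to each patient will be estimated using utilization information from HCI financial/claims data". Section 8.4 adds "We will utilize available CPT code charges generated from the time of registration to 2-8 weeks after the completion of radiation therapy" and "We will utilize the HCI financial data to estimate reimbursable charges". It expects direct cost to fall through "an expected reduction in health care utilizations services (e.g., office visits, emergency room visits, inpatient admissions".

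Section 9.2.4 sets the scope: "A societal perspective will be applied for the analysis because the direct costs", the indirect costs and the side-effect costs are all to be counted. Besides the therapy itself, it lists drugs, inpatient stays and visits. It then says "Costs for treatments due to side effects will be collected", without naming an instrument, and "We will not compare charges or costs between institutions".

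The patient-reported source is the Appendix II survey. It covers work, travel time and distance, transport, lodging, companions, lost work, child care and lost wages. Its single count of health-care use is "Number of visits to radiation treatment facility since completing radiation therapy (follow up visits". The Appendix III diary is, by footnote 4 of the study calendar (section 7), an aid to recall for that survey. For the 45 comparators, section 8.4 describes the survey and no diary.

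**The concern.** The savings in health-care use that section 8.4 expects are seen only when HCI bills for them. A woman who goes to a local emergency department, is admitted elsewhere, sees her own physician or buys medicines at a pharmacy for a radiation side effect generates cost that a societal analysis should count. No named source records that cost for both groups. If the plan is followed as written, a cost billed by one institution, plus travel and time, will be reported as societal, and a statement about total use of health services would lack data behind it. The cost-effectiveness ratio and acceptability curve would carry the same label. The primary cosmetic endpoint is not affected.

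**Working it through.** **1. Cost items against sources.**

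| Cost item | Raised in | Named direct-cost source | Appendix II item |
|---|---|---|---|
| Radiation therapy | 9.2.4 | HCI data, charges | not needed |
| Office visits | 8.4, 9.2.4 | HCI data, charges | radiation facility only |
| Emergency visits | 8.4 | HCI data, charges | none |
| Admissions | 8.4, 9.2.4 | HCI data, charges | none |
| Medicines | 9.2.4 | HCI data, charges | none |
| Side-effect treatment | 9.2.4 | no instrument named | none |

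Of the four kinds of outside care (emergency visits, admissions, other office visits, medicines), the survey covers 0 of 4.

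**2. Adverse-event records.** Sections 12.4.1 and 12.4.2 record adverse events of every grade until year 3. The action field includes hospitalization and concomitant medication, and qualifying admissions are reported as serious events. Nothing limits this to care at HCI. However, section 9.2.4 does not link these records to costing, and they exist for trial patients only. Section 9.2.2 draws a toxicity comparison group from a database, but does not say that these are the 45 cost comparators or that outside treatment is recorded. Costing adverse-event data alone would therefore count care more fully in the 9-fraction group.

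**3. Does the shorter course fix a direction?** Start with the plan's own figure. The Study Summary gives 11-14 calendar days for 9 fractions. Counting weekdays only, 9 fractions span 11 days (Monday or Tuesday start) or 13 days (other starts), and a one-day break can make it 14, so the figure reproduces. Nineteen fractions span 25 or 27 days. For the same start day the difference is 14 days.

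Assume, for illustration, that need is even over time, that all care during treatment is at HCI, and that a share q of care in the 40 days after treatment is elsewhere. The 40 days come from the lost-work question in Appendix II; q is not in the documents.

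- Missed care = q × 40 days in each group. At q = 30% that is 12 days in both, so the difference in missed care is 0.
- Missed share = 12/51 = 23.5% for 9 fractions (11 + 40 days) and 12/65 = 18.5% for 19 fractions (25 + 40 days). The shares differ only because the denominators do.
- If instead both groups are given the same true total of $1,000, the gap is $1,000 × q × (40/51 − 40/65) = $1,000 × 0.169q: $17 at q = 10%, $51 at 30%, $84 at 50%, in favour of 9 fractions.
- If a share s of all care is outside HCI in both groups, the measured difference is (1 − s) × the true difference. Any true saving is understated by s, that is by 10-50% for an assumed s of 10-50%.
- If adverse-event data were costed for trial patients only, measured cost would rise in the 9-fraction group alone, against the hypothesis.

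These assumptions give no bias, bias towards the hypothesis, attenuation, and bias against it. The documents do not choose between them.

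**The case against.** The other side has several fair arguments.

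- *Outside care is not invisible.* This stands for trial patients, because of the adverse-event records. It does not supply a cost or reach the comparators.
- *Claims data may include payer claims.* Section 9.2.4 does mention plan-paid amounts. But no payer source is named, and section 8.4 prices from HCI data. If outside claims will be obtained, one sentence saying so would largely settle the point.
- *The diary asks for expenses connected with health care.* Its fields are not visible in the text available, so what it leaves out cannot be asserted. What can be said is that no step collects or costs its entries.
- *The survey is not silent on facility stays.* It has a tick-box for having been in a health care facility during radiation. That box describes where the patient was living; it neither counts admissions nor covers the period afterwards.
- *Proportion.* The analysis is secondary and exploratory, and the main contrast, 9 versus 19 treatments, is in HCI billing. This limits the importance of the point; it does not justify the societal label.

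A reader might infer something stronger: that 9-fraction patients go home sooner, so more of their care is missed and the comparison leans towards the hypothesis. The documents do not support this. They do not say where patients seek care. The post-treatment window is nominally 2-8 weeks in both groups, and comparators are matched on travel distance and employment. The remark in section 2.1 about women living far away concerns the once-weekly UK FAST schedule, not this trial's patients. Under even need, the same absolute amount is missed in both groups.

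**Conclusion.** The point holds as a gap between the scope claimed in section 9.2.4 and the sources named in sections 2.6 and 8.4 and Appendix II. Care obtained outside HCI is under-measured, and the resulting figure is not a societal cost. This rests on two readings: that HCI financial and claims data do not include other providers' claims, and that diary entries reach the analysis only through the survey. The size and direction of any effect on the cost difference cannot be determined from the documents; the dollar figures above illustrate assumptions and are not estimates. A bias caused by the shorter schedule should not be asserted. The matter should be settled before economic results are reported.

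**What to change.** Add four items to Appendix II, worded identically for trial patients and the 45 comparators: the number of emergency visits, admissions and office visits outside HCI, and out-of-pocket medicines for radiation side effects. Value them at HCI unit costs, which avoids bringing in other institutions' prices.

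Use the same window in both groups. The documents now give three end points: 2-8 weeks after radiation (section 8.4), 40 days (Appendix II lost-work question) and 6-10 weeks (Appendix III). A survey completed at 2 weeks (14 days) cannot cover 40 days, so these need reconciling first.

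State in section 9.2.4 that adverse-event data will not be costed for one group only.

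Where surveys are already complete, replace the societal perspective in section 9.2.4 with: *HCI-billed direct costs plus patient-reported travel, time and other out-of-pocket costs*. Make no claim about total health-care utilisation.

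The cost is a slightly longer survey, one more cost line and a minor amendment. The new items carry self-report error, and nothing can be recovered for surveys already completed. The wording change needs no new data.
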